Based on this hypothesis, we already investigated the prognostic significance of peripheral blood immune cell counts in HR+/HER2- aBC patients treated with ET+CDK4/6i. 42 In fact, although the main mechanism of CDK4/6i-mediated anticancer activity consists in cell autonomous anticancer effects, preclinical evidence indicates the CDK4/6i ability to stimulate antitumor immunity. To preliminary investigate if peripheral blood immune cell counts or composite immune parameters, as evaluated at baseline or during CDK4/6i therapy, are associated with efficacy of any-line ET+CDK4/6i, we performed an analysis in 638 HR+/HER2- aBC patients treated in six Italian centers. In this study (PALMARES study), we investigated if baseline or ontreatment peripheral blood immune cells, such as lymphocytes, neutrophils, platelets or monocytes, or the composite scores neutrophil-to-lymphocyte ratio (NLR), platelet-to-lymphocyte ratio (PLR), monocyte-tolymphocyte ratio (MLR) or the Pan-Immune Inflammatory Value (PIV), are associated with patient PFS. Peripheral blood immune cell values were collected at baseline (T0), 2 weeks after treatment initiation (T1) and before fourth cycle initiation, approximately 12 weeks after treatment initiation (T2). We used Random Forest models to select clinically relevant covariates (line of therapy for advanced disease, ECOG PS, presence of liver metastases, number of metastatic sites, patient age, disease-free interval (DFI), percentage of Ki-67-positive cells in primary tumor specimens and presence of ER expression in primary tumor specimens) to adjust the role of peripheral blood immune cells in multivariable cox models. Median patient age in this cohort of patients was 61 years (IQR: 52-70 years). The majority of patients were postmenopausal (n=530; 83.1%), had an ECOG PS of 0 (n=464, 72.8%) and were treated with palbociclib (n=529; 82.9%). Approximately half of enrolled patients received CDK4/6i in the first-line setting (n=335; 52.5%) and had visceral disease (n=334; 52.4%). Among all the considered peripheral blood immune variables (neutrophils, platelets, lymphocytes and monocytes, the NLR, the PLR, the MLR and also the PIV), only baseline lymphocyte values and their precocious modulation (i.e. after 2 weeks of treatment), were independently associated with patient PFS.42

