we conducted a subanalysis on the PALMARES study cohort treated with first-line CDK4/6i plus ET. HER2 status was available for 428 patients in the study cohort. We found that patients with HR+/HER2-low aBC had significantly worse PFS (mPFS 23.6 months vs. 32.3 months; p=0.014) and OS (mOS: 48.7 vs 58.3 months; p=0.029) when compared to patients with HER2-0 aBC. Multivariable analysis confirmed an independent association between HER2-low status and worse PFS (aHR 1.42; 95% CI:1.07-1.89; p=0.016) and OS (aHR: 1.64; 95% CI: 1.08-2.48; p=0.02).⁴⁸ However, another large study conducted by Mouabbi J. et al investigated the prognostic role of HER2 status in 1649 HR+/HER2- aBC patients treated with ET in combination with different targeted therapies (CDK4/6i, everolimus or alpelisib). In the sub-cohort of 919 patients treated with CDK4/6i plus ET, there were no statistically significant differences between patients with HER2-low and HER2-0 aBC in terms of PFS (13.0 vs 11.6 months, p=0.273) and OS (32.4 vs 31.2 months, p=0.222).⁴⁹ The reported discrepancies among published studies, in addition to the increased value of the HER2-low status in the treatment of HR+/HER2- aBC, laid the foundations for further investigations on this potentially useful and easy-to-access biomarker.

To summarize, our previous preliminary results, together with available literature, demonstrated that some biomarkers already available in clinical practice could be potentially used to distinguish different prognostic classes of HR+/HER2- aBC patients treated with first-line ET+CDK4/6i. However, larger studies are necessary to confirm available results and finally implement in clinical practice novel treatment biomarkers.

Differences between the three CDK4/6i drugs in combination with ET and their impact on efficacy

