PALMARES-2 is a retrospective/prospective, observational, multicenter, population-based study, aiming at providing real-world evidences on HR+/HER2- aBC patients treated with first-line CDK4/6i plus ET.

The present study has the objective to collect data coming from different sources, i.e. RWD, medical images and biological samples, from patients treated with CDK4/6i as first-line of therapy for HR+/HER2- aBC. In consideration of the complexity of data collected and different objectives of the study, this master protocol foresees different sub-studies, which encompasses different methodologies for data collection, data extraction and analyses. The sub-studies will be described in the following sections.

[figure not shown]

Figure 1. PALMARES-2 graphical abstract. CBC: cell blood count; CT: computed tomography; ET+CDK4/6i: endocrine therapy plus cyclin-dependent kinase 4/6 inhibitor; FdG-PET: fluorodeoxyglucose positron emission tomography; FFPE: formalin-fixed paraffin-embedded; HE: hematoxylin-eosin; HR+/HER2- aBC: hormone receptor-positive, human epidermal growth factor receptor 2-negative advanced breast cancer; PD: progressive disease; RWD: real-world data.

(1) Real world data (RWD) PALMARES-2 sub-study

Objectives and endpoints of the sub-study:

Primary objectives:

- To test the difference in terms of OS between the group of patients receiving ribociclib and palbociclib;
- To test the difference in terms of OS between the group of patients receiving abemaciclib and palbociclib.

Secondary objectives:

- To test the difference in terms of OS between the group of patients receiving abemaciclib and ribociclib.
- To determine the real-world progression-free survival (rwPFS), time to next treatment or death (TTNT-D), time to chemotherapy or death (TTC-D) and OS in the real-world setting;
- To test the difference in terms of rwPFS between the group of patients receiving ribociclib and palbociclib;
- To test the difference in terms of rwPFS between the group of patients receiving abemaciclib and palbociclib;
- To test the difference in terms of rwPFS between the group of patients receiving abemaciclib and ribociclib;
- To test the difference in terms of TTNT-D between the group of patients receiving ribociclib and palbociclib;
- To test the difference in terms of TTNT-D between the group of patients receiving abemaciclib and palbociclib;
- To test the difference in terms of TTNT-D between the group of patients receiving abemaciclib and ribociclib;

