The study involves the collection of RWD, i.e. obtained directly from the medical records, electronic or paper, of the patients enrolled in the study. Therefore, no additional patient assessment will be required specifically for study purposes. Data will be collected locally within the center participating in the study, subject to patient consent, and then reported on a platform in .xlsx format.

The types of data collected within this sub-study include:

- Demographic data: date of birth, gender, menopausal status;
- Neoplasm history data: de novo vs metachronous presentation; date of diagnosis of localised disease; prior treatment for localised disease, including type and duration of prior hormonal, chemotherapy and CDK4/6i treatment; number and type of metastatic sites;
- CDK4/6i treatment data: drug used; backbone of hormone therapy and date of initiation of hormone therapy versus initiation of CDK4/6i; use of LHRH analogue;
- Tumor biology data: hormone receptor status, grading, proliferation index at biopsy site of metastasis and, if not available, relative to primary tumor; OncotypeDX;
- Data on haematochemical parameters: complete bloodcounts and some biochemical parameters such as LDH, blood glucose and CA15.3, collected at baseline, 15 days after starting CDK4/6i, after 30 days and at treatment progression;
- Genomic data: genomic alterations available to the patient, performed according to clinical practice; this section includes both somatic mutations and germline DNA alterations.

(2) Toxicity – Comorbidity sub-study

The "toxicity – comorbidity" sub-study aims to add a key piece to the real-world evidence of the three CDK4/6i, allowing for the first time a systematic comparison of the real-world toxicities of palbociclib, ribociclib and abemaciclib.

Objectives and endpoints of the sub-study

Primary objective:

To compare the real-world incidence of severe toxicity, defined as a grade 3 or higher adverse event reported by the clinician, occurring during treatment, among the three CDK4/6i.

Secondary objectives:

- To compare the real-world incidence of overall toxicity, defined as any-grade adverse event reported by the clinician, occurring during treatment, among the three CDK4/6i;
- To assess the incidence of dose reduction conditioning toxicity;
- To assess the incidence of toxicity requiring discontinuation of treatment or switch to another molecule of the CDK4/6i class;

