For the "Translational sub-study" purposes, tumor samples related to patients enrolled in the RWD sub-study will be considered. If multiple tumor samples are available, the ones to be used for the study has to be chosen as specified in the section "Translational sub-study". Tumor materials have to be shipped to the Sponsor center at the moment of the conduction of translational analyses, attributing the same pseudonymized code used for the other sub-study. The remaining unused tumor tissue will be sent back to the pathology laboratory at the end of the study.

Statistical considerations

Statistical design

Based on pivotal trials showing a statistically significant OS advantage for ribociclib and abemaciclib, but not for palbociclib in the endocrine resistant setting, and clinically meaningful OS advantage for ribociclib and abemaciclib, but not for palbociclib in the endocrine sensitive setting, we will hypothesize a difference of 20% in terms of OS between ribociclib versus palbociclib and between abemaciclib and palbociclib. To detect this difference with 80% power with a two-sided alpha error of 0.05, a sample size of 3258 patients reaching 977 OS events will be required. The prognostic role of CDK4/6i drug will be weighed for clinically and biologically relevant characteristics.⁸⁹

Since the number of patients enrolled in the other sub-studies depends on the sample size of the RWD sub-study, no formal statistical calculation has been performed for 2 to 5 PALMARES-2 sub-studies.

Statistical methods

Version 1.1, 01Aug2024

Standard descriptive statistics will be used to describe clinical and biological patients' characteristics. The median and interquartile range (IQR) were reported for continuous variables. Categorical variables were summarized as percentages of available data. To evaluate differences, in terms of clinic-pathological characteristics, among different CDK4/6i groups, we will use the Kruskal-Wallis Rank Sum test for

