continuous variables and the Chi-square and Fisher exact tests for categorical variables. Unpaired t-test will be used to compare numeric variables, at baseline and different timepoints. Classic survival analysis methods will be used to evaluate patient survival outcomes and survival curves will be obtained through the Kaplan–Meier method. Follow-up times will be estimated using the reverse Kaplan–Meier method. Multivariable analysis will be performed through Cox regression modeling to estimate the effects of covariates. To homogenize patients' characteristics among treatment groups, additional adjustment techniques will be eventually used, such as propensity score matching (PSM) and inverse probability of treatment weighting (IPTW). Estimated weights will be then incorporated into a weighted Cox regression model to estimate rwPFS. Area Under the ROC Curve (AUC) values of the models will be calculated using the Caret and pROC R package and compared using Delong's test.

Patients with missing outcome data will be excluded from the analysis. Covariates whose values will be missing in less than 20% were imputed by using the median or the mode value (for numerical or categorical variables, respectively), while covariates with missing values exceeding 20% will be excluded from the present analysis. 90 All statistical tests will two-tailed, and a p value (P) <0.05 was considered as significant. Statistical analyses will be performed using R software and R Studio (version 4.1.2).

Image omics and model generation methodology

Radiomics Methodology

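### Dropping every covariate with more than 20% missing values, and filling the others with one median or mode, can leave confounding in the non-randomised primary OS comparisons

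*Protocol*

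**What the plan says.** The first primary objective of the RWD sub-study is "To test the difference in terms of OS between the group of patients receiving ribociclib and palbociclib". The second is the same comparison for abemaciclib against palbociclib. The design is observational, with drugs given as in clinical practice.

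Statistical design says: "The prognostic role of CDK4/6i drug will be weighed for clinically and biologically relevant characteristics". Statistical methods names multivariable Cox regression, with propensity-score matching or inverse probability weighting as possible additions.

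Statistical methods then fixes two rules for missing covariates:

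- Below the threshold: "Covariates whose values will be missing in less than 20% were imputed by using the median or the mode value".
- Above it: "while covariates with missing values exceeding 20% will be excluded from the present analysis".

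Neither rule has an exception for covariates that drive drug choice or survival.

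**The concern.** In a non-randomised comparison, an unadjusted difference in prognosis between the drug groups appears as a drug effect. Whether a covariate is needed depends on its link with drug choice and with survival. The share of missing values says nothing about either. Under the deletion rule, a strong confounder recorded in three quarters of patients is left out of the adjustment entirely. Under the filling rule, everyone with a missing value gets the same value, so adjustment for that covariate is only partial.

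The bias can go either way: it can create an apparent OS difference or hide a real one. The Protocol's own background section faults an earlier national real-world comparison for having too few patient characteristics, biological ones among them, to correct for confounding by drug choice. The deletion rule can recreate that gap by design.

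**Working it through.** **1. The plan's own figure.** The 20% missingness cut-off has no calculation behind it. The relevant stated figure is 3258 patients with 977 OS events (977/3258 = 30%) for a 20% difference at 80% power and two-sided 5%, where (1.960 + 0.842)² = 7.849.

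- Freedman, HR 1.2, 1:1: 7.849 × (2.2/0.2)² = 950 events, and 950/0.30 is about 3,167 patients. This is within 3% of the stated figures.
- Schoenfeld, HR 0.80, 1:1: 4 × 7.849/(ln 0.80)² = 631 events. This reaches 986 only with a 20:80 split.

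The scale of the 20% is not stated, so both readings are used as benchmarks in step 4.

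**2. Assumed inputs.** The Protocol gives no missingness, imbalance or allocation figures. Assumed throughout: true drug HR 1.00 and one binary confounder. Confounder HRs are 2.0 and 2.5, plus 1.64, which is the adjusted OS HR that the background gives for HER2-low and is used here for strength only. Prevalence (palbociclib versus the other drug) is 40% versus 20% (strong imbalance) or 30% versus 25% (mild).

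**3. Bias from deletion.** To a close approximation the apparent drug HR is [1 + p₁(HR − 1)]/[1 + p₀(HR − 1)], with p₁ for the other drug and p₀ for palbociclib. At 40% versus 20% with HR 2.0 this is 1.2/1.4 = 0.857.

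The simulation used 800 cohorts per scenario, 35% of patients on the comparator, exponential survival with reference median 65 months, uniform censoring at 3 to 56 months and 29–34% events.

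| Prevalence | Confounder HR | Formula | Simulated |
|---|---|---|---|
| 40% vs 20% | 1.64 | 0.898 | 0.90 |
| 40% vs 20% | 2.0 | 0.857 | 0.86 |
| 40% vs 20% | 2.5 | 0.813 | 0.82 |
| 30% vs 25% | 1.64 | 0.973 | 0.98–0.97 |
| 30% vs 25% | 2.0 | 0.962 | 0.96 |
| 30% vs 25% | 2.5 | 0.948 | 0.95 |

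With the strong imbalance reversed, the HR is 1.15–1.22 for confounder HR 2.0–2.5. If one retained covariate is correlated about 0.5 with the deleted one, the strong case weakens to 0.89–0.86. A 50:50 split changes little (0.865 and 0.824).

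**4. Size against the planned effect (strong imbalance).** ln(0.90)/ln(0.80) = 47%, ln(0.86)/ln(0.80) = 68% and ln(0.82)/ln(0.80) = 89%. With the retained correlated covariate it is 52–68%. Read against HR 1.2, the first three become 58%, 83% and 109%.

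**5. False-positive rate after deletion (nominal 5%).** The Protocol does not say whether 3258 is the size of one pair or of all three groups, so both readings are shown.

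- Strong imbalance, confounder HR 2.0–2.5, simulated: about 42–72% if a pair holds two-thirds of the patients, and 58–85% if it holds all.
- Strong imbalance, confounder HR 1.64, by normal approximation: with 977 × 2/3 = 651 events, SE = 1/√(651 × 0.35 × 0.65) = 0.082. Then |ln 0.898|/0.082 = 1.31, a rate of about 26%. With 977 events, SE = 0.067, the ratio is 1.60 and the rate about 36%.
- Mild imbalance: 5–12%.

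**6. Filling at 19% missing.** At 40% versus 20% the apparent HR is 0.97 for confounder HR 1.64 and 0.96–0.95 for HR 2.0–2.5. At 30% versus 25% it is 0.99. The standard error is not the problem: after filling, the mean model SE was 0.0676 against an empirical SD of 0.0680.

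**7. Multiple imputation.** The imputation model contained drug, event indicator and cumulative hazard, with pooling by Rubin's rules. With data missing at random, the HR was 0.99–1.00 at 19%, 25%, 40% and 60% missing, and the false-positive rate 4–6%.

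**8. Check with other inputs.** A separate simulation used a 1:1 split and N = 3258, with missingness differing by drug group.

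| Confounder | Missing | Rule in the plan | Multiple imputation |
|---|---|---|---|
| HR 2.0, 45% vs 25% | 30% | Deleted: 0.86 (66.5% false positives) | 1.00 (4.5%) |
| HR 1.5, 40% vs 30% | 30% | Deleted: 0.96 (10.5%) | 1.00 (4.8%) |
| HR 2.0, 45% vs 25% | 19% | Filled: 0.93 (21%) | 0.99 (6.0%) |
| HR 1.5, 40% vs 30% | 19% | Filled: 0.97 (7.2%) | 1.00 (5.2%) |

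**The case against.** **Nothing shows that the rule will bite.** No figure in the Protocol puts a confounder above 20% missing. In the group's earlier cohort the core clinical covariates look nearly complete: 530/638 = 83.1% and 334/638 = 52.4% agree with the printed percentages, and 464 printed as 72.8% fits a base of 637. The data-collection wording "proliferation index at biopsy site of metastasis and, if not available, relative to primary tumor" is a fallback that reduces gaps, and "Categorical variables were summarized as percentages of available data" is routine descriptive language. All of this stands. Biological covariates remain the more likely casualties, since the data come from routine records with no study-specific assessments, but how often this happens is unknown.

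**HER2 is a poor example.** The background says "HER2 status was available for 428 patients in the study cohort". Against 638 that would be 33% missing. However, 638 covers any line of therapy, the earlier report counts only 335 first-line patients, and eligibility here requires a HER2 result. The figure carries almost no weight, and the conclusion does not use it.

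**The large biases need strong imbalance and one dominant confounder.** This is true. Retained correlated covariates reduce the bias, and under mild imbalance it is small. Filling alone then does almost no harm.

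**Multiple imputation can fail too.** Suppose values are missing in 45% of confounder-positive patients of one drug group and in 15% of everyone else. Multiple imputation then gave 0.93–0.91 or 1.04–1.06, depending on the group. Filling gave 0.89–0.86 or, by cancellation, 1.00–1.01. Complete-case analysis gave 1.00 in both. This limitation is real and is the reason for the complete-case analysis in the fix.

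**Details belong in the SAP.** A covariate list may well appear there. The two rules, however, are fixed in the Protocol without exception, and the concern is with those rules.

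**Conclusion.** The concern holds. Followed as written, the deletion rule can bias both primary OS comparisons in either direction. The bias reaches 47–89% of the planned effect (read as HR 0.80) under strong imbalance and is small under mild imbalance. Filling is the lesser problem.

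Confidence is high that the rule is stated and can have this effect. The sizes are illustrative: they rest on an assumed single binary confounder, assumed prevalences and strengths, and no true drug effect. The plan should be changed, because the rule ignores confounding strength and a better method costs little.

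**What to change.** In Statistical methods, for the adjustment covariates of the drug comparisons:

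1. Replace both rules with multiple imputation. Include drug, event indicator and cumulative hazard in the imputation model, fit the Cox or weighted model within each imputed set, and pool with Rubin's rules.
2. Keep pre-specified confounders whatever their missing share. If one is missing in more than about 60% (the highest share simulated, so a limit of the evidence and not a natural threshold), report results with and without it.
3. Add a complete-case sensitivity analysis, because multiple imputation relies on data missing at random.

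The cost is Protocol wording and computing, repeated for each time-to-event endpoint because the imputation model contains the outcome. No new data are needed. Compared with full data, the standard error of the drug effect rises by 1–2% at 19% missing, 3–5% at 40% and 6–9% at 60%. Where missingness depends only on the confounder (30% versus 15%), multiple imputation gave 0.99–0.98. If it depends on both confounder and drug, some bias remains, and comparison with the complete-case result can help to reveal it.

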Clinical real world data will be collected by centers in ad hoc document in .xlsx format. At pre-specified data cut-off (see sections below), data collected will be shared with the Sponsor for data analyses. Investigators at study centers could be required to modify data in case of data inconsistencies encountered during data analyses.

All consecutive HR+ HER2- aBC patients treated with first-line ET plus CDK 4/6i as per clinical practice in the time interval between January 2017 and December 2030 will be enrolled retrospectively and prospectively. Data will be collected in a continuous manner and will be shared with the Sponsor center on an annual basis, at pre-specified data cut-offs. Data cut-offs will occur annually, at certain cutoffs falling on 1st January of each year. Taking into account the time interval and the centers involved, approximately 2000 patients will be included at the first data cut-off of 1st January 2024. Those patients who have already concluded the treatment at the time of study inclusion will be evaluated for clinical outcomes (i.e. PFS, OS) and biological parameters of interest will be retrospectively collected. Patients who are still receiving ET plus CDK4/6i at the time of inclusion in the study will be evaluated for the same variables until the end of the study. At the time of data collection and analysis, these patients will be censored for the events of interest (e.g. progression, death) if these events have not occurred yet.

[figure not shown]

Figure 2. PALMARES-2 study expected timeline and enrollment. EC: ethical committee; pts: patients.

Medical images collection and sharing

The medical images, collected within the timeframe specified in the appropriate section (see section "Medical images sub-study"), will be collected locally in the individual centers, pseudonymised and uploaded to an ad hoc secure sharepoint. A folder will be set up for each individual center participating in this sub-study, so that only the center uploading the images and the Sponsor center itself will be able to access them.

Tumor samples collection, storage and shipment

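### Two primary OS contrasts share the palbociclib group and are each judged at unadjusted p<0.05, so 0.05 is a per-contrast rate and the chance of a false primary claim is about 9%

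*Protocol*

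**What the plan says.** The primary objectives of the RWD sub-study are two separate OS comparisons with a common reference group: "To test the difference in terms of OS between the group of patients receiving ribociclib and palbociclib" and "To test the difference in terms of OS between the group of patients receiving abemaciclib and palbociclib". Abemaciclib against ribociclib is secondary.

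Statistical design hypothesises a 20% difference in OS for both contrasts and sizes the study once: "To detect this difference with 80% power with a two-sided alpha error of 0.05, a sample size of 3258 patients reaching 977 OS events". It does not divide alpha, order the contrasts, or require both to succeed.

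Statistical methods sets a two-tailed decision rule for all tests in the protocol: "a p value (P) <0.05 was considered as significant".

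On timing, Clinical data collection and management states: "At pre-specified data cut-off (see sections below), data collected will be shared with the Sponsor for data analyses". It adds: "Data cut-offs will occur annually, at certain cutoffs falling on 1st January of each year". About 2000 patients are expected at the first cut-off, 1 January 2024. No endpoint or test is assigned to any cut-off.

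**The concern.** A reader who sees one alpha of 0.05 in the design will take it as the chance of a wrong primary conclusion. With two primary contrasts, either of which can be claimed alone, it is not. The between-drug OS comparison is the main claim of the RWD sub-study and the basis of its sample size, so the error rate attached to it should be stated correctly.

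Timing adds a second, conditional issue. The first cut-off falls at about 2000/3258 = 61% of the target patients, so data reach the sponsor for analysis well before the target size. The p<0.05 rule makes no distinction between an OS comparison made then and one made at 977 deaths.

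**Working it through.** **Inputs from the protocol.** Two primary contrasts with a shared comparator; two-sided 0.05; 80% power; 977 events in 3258 patients; p<0.05 for all tests.

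**Assumptions of this check.** Drug shares of events are not given, so I use equal thirds and 50/35/15 (palbociclib/ribociclib/abemaciclib). The scale of the 20% is not given, so I try hazard ratios of 0.80 and 1.20. Each test is taken to hold its nominal 5% after adjustment for confounding.

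**1. The plan's own figure.** 977/3258 = 0.300, so N follows from 977 events at a 30% event proportion, which is implied but not stated. With (1.960 + 0.842)² = 7.849:

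- Freedman, HR 1.20, 1:1: 7.849 × (2.2/0.2)² = 950.
- Freedman, HR 0.80, three equal arms: 7.849 × (1.8/0.2)² = 636, and 636 × 1.5 = 954.
- Schoenfeld, HR 1.20, 41:59 split: 7.849/(0.41 × 0.59 × ln(1.2)²) = 977 (rounded up).

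So 977 is reproduced within 3% at the unadjusted 0.05 under several readings. With 0.025 two-sided per contrast and 1:1 allocation, the requirement would be 764 to 770 (HR 0.80) or 1144 to 1151 (HR 1.20). The figure is consistent with no adjustment having been built in.

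**2. Familywise rate at one analysis.** The correlation of the two test statistics, where d is the event share of each drug, is

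ρ = (1/d_P) / √[(1/d_P + 1/d_R)(1/d_P + 1/d_A)]

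- Equal thirds: 3/√(6 × 6) = 0.50.
- 50/35/15: 2/√(4.857 × 8.667) = 0.31.

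The rate is 1 − P(|Z₁| < 1.96 and |Z₂| < 1.96):

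| Case | Chance of at least one false primary claim |
|---|---|
| ρ = 0.50 | 1 − 0.9093 = 0.091 |
| ρ = 0.31 | 0.095 |
| Independent | 1 − 0.95² = 0.0975 |
| Upper bound | 0.05 + 0.05 = 0.10 |

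This needs no assumption about repeated looks.

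**3. Conditional: both contrasts also tested at p<0.05 at earlier cut-offs.** By simulation under no difference, counting a claim at any look. The range covers the two drug mixes.

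| Assumed looks (fraction of final events) | Either contrast |
|---|---|
| 0.8, 1 | 0.126 to 0.133 |
| 0.6, 0.8, 1 | 0.161 to 0.169 |
| three equally spaced (equal thirds only) | 0.189 |

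The result moves with the schedule, and the protocol gives no schedule for testing OS.

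**4. Price of control.** Take the plan's 80% per contrast at 977 events as given, so the expected Z is 1.960 + 0.842 = 2.802.

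- Bonferroni at 0.025 (critical value 2.241): Φ(2.802 − 2.241) = 0.71. Restoring 80% multiplies events by (2.241 + 0.842)²/7.849 = 1.211, about 1184 events.
- Holm, both effects real: power per contrast is P(Z₁ > 2.241, or Z₁ > 1.960 and Z₂ > 2.241). This is 0.764 at ρ = 0.50. With independence it is 0.712 + (0.800 − 0.712) × 0.712 = 0.775. If only one effect is real, Holm gives about 0.71 for it.
- Fixed order, ρ = 0.50: 0.80 for the first contrast and 0.69 for the second, because both must pass.

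**The case against.** Three points can be made for the plan.

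First, the protocol never calls its 0.05 familywise. The two contrasts concern different drugs and are listed as separate objectives. Treating them as two questions at 0.05 each is a defensible position, particularly in an observational cohort. That stands, but the protocol does not take this position in words. It gives a single alpha for a single sample size covering both.

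Second, a reader might infer that the primary OS contrasts are tested at every annual cut-off, and hence that the error rate is two to four times 0.05. The documents do not support this. The text describes a yearly transfer of data for unspecified analyses in a master protocol with five sub-studies, and it names no OS test at a cut-off. The target of 977 deaths is compatible with one event-driven analysis. This objection stands in full, and the figures for two or more looks are illustrations only.

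Third, the timing of the primary test is commonly left to a statistical analysis plan, which is not shown here; the timeline figure is not shown either. So the absence of a named cut-off is not a fault in itself. What the protocol does fix is p<0.05 for all tests. A later document that adjusted the primary contrasts would have to depart from that sentence.

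**Conclusion.** The point holds for the two contrasts. Following the plan as written, the chance of at least one false primary OS claim at a single analysis is about 9 to 9.5%, nearly twice the stated alpha and never above 10%. This rests only on the two objectives, the shared palbociclib group and the p<0.05 rule; the drug mix moves it by about half a percentage point.

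The point about annual cut-offs is narrower: the rule as worded leaves room for OS testing before 977 deaths. If that happened without adjustment, the rate would be about 13% with looks at 80% and 100% of events, or 16 to 17% with looks at 60%, 80% and 100%. Those schedules are assumed. The sponsor should settle the matter before OS is compared at further cut-offs. It does not invalidate the design.

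**What to change.** 1. Define the primary OS analysis as the first annual cut-off at which 977 OS events have been reached.
2. Label OS comparisons between drugs at earlier cut-offs as descriptive. If they are to be tested, add an alpha-spending function.
3. Test the two primary contrasts with Holm at a familywise 0.05 and exempt them from the general p<0.05 sentence. Alternatively, state that 0.05 is per contrast and report the familywise rate of roughly 9% beside it.
4. Restate the power to match.

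The cost is a few sentences and some power. At 977 events with both effects real, Holm gives about 76 to 77% per contrast instead of 80%. A fixed order keeps 80% for the first contrast and gives about 69% for the second at correlation 0.5. Plain Bonferroni gives about 71% and would need about 1184 events to restore 80%, so it is the least attractive of the three. Declaring 0.05 as per contrast costs no power, only the explicit statement of the familywise rate.
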